# 2 Introduction

# 2.1 Background

Whilst there is a large body of literature examining weight loss, there are few randomised controlled trials specifically exploring maintenance. One RCT of weight loss maintenance found that at 18 months in the intervention group average weight gain was 2.5kg whereas in the control group average gain was 4.9kg. Another study with a longer follow-up found that at 30 months those in the intervention group had a mean regain of 4kg compared to 5.5kg in the control group and 71% remained below entry weight. Although there is some evidence which indicates that maintenance interventions are associated with smaller weight gains compared to no contact, he prevention of weight regain remains a challenge, differences between intervention and controls tend to be small and around a third of the weight lost during an intervention is regained in the following year.

The psychological processes, skills and strategies which are likely to be effective for weight maintenance are potentially different from those that are needed to lose weight. A Research examining 5000 people on the National Weight Control Register suggests that the only factor those losing weight have in common is that they combined diet and exercise to lose weight. When examining the maintenance phase however, a number of common factors were identified including low fat diet, eating breakfast, self monitoring and high levels of physical activity. Losing weight requires a negative energy balance whereas weight maintenance requires continued energy balance. This balance needs to be sustained by behaviours which can be continued over the longer term. In reviews of factors associated with weight loss maintenance a number of issues stand out which are central to the current intervention. These are higher levels of physical activity, low calorie and low fat foods, tailoring of advice, self regulation/monitoring, social support, internal motivation and self efficacy.

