# 6.5 Withdrawal & loss to follow-up

Participants have the right to withdraw consent for participation in any aspect of this trial at any time. In order to ascertain which aspect the participant wishes to withdraw from, withdrawal forms will be completed by the study team. If participants wish to withdraw from all aspects of the study without giving reason, consent to use data already collected will be assumed unless otherwise specified. Care from health services will not be affected at any time by declining to participate or withdrawing from the trial. Based on systematic reviews of similar studies we estimate that loss to follow-up will be around  $30\%^{17,39,40}$ .

We will make every effort to reduce loss to follow-up using the methods listed below:

- 1. We will emphasise the importance of getting follow-up data to all participants at baseline and the 4 different follow-up points.
- 2. Unless they have explicitly requested otherwise, all participants will be invited to complete follow-up questionnaires and attend follow-up appointments.
- 3. We are seeing people face to face for all the assessments except at six months.
- 4. We will arrange to complete follow-ups in the participants' homes or somewhere convenient to them so they won't have to travel far.
- 5. We will have regular contacts in the two intervention arms building relationships with participants. We will also send newsletters and birthday cards with a 'change of address' form to participants in all 3 trial arms.

19

- 6. Participants in the control group will be offered £50 in high street vouchers or a free 12 week attendance at a local Slimming World or Weight Watchers programme at the end of the follow-up as an additional incentive to complete follow-up.
- 7. We will send two reminders to ask participants to return the postal questionnaire and will rearrange follow-ups twice for those who do not attend an arranged appointment.
- 8. We will obtain participants mobile phone numbers so we can contact them directly to arrange follow-up.
- 9. We will ask the participants for their GP address as well as alternative contacts.
- 10. We will look at the choice of outcomes to minimise respondent burden.
- 11. We will complete over the telephone the key questionnaires for non-responders so we have a minimum data set.

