#### 11 Analysis

#### 11.1 Main analysis

The main outcomes relate to the feasibility of the study. Descriptive statistics relating to the patient recruitment, compliance and retention and well as intervention delivery will be presented.

Given the recruitment issues it is unlikely that we will find a significant difference unless the impact of this intervention is far greater than other types of intervention in this group. So the main analyses will be completed for the study as a feasibility study. We will also examine the point estimates of effectiveness and their confidence intervals for BMI. We

will analyse for key secondary outcomes that are more immediate targets of the intervention (e.g. self-efficacy) to consider the potential of the intervention, as well as assessing if there is a trend from no intervention to the intensive intervention with the less intensive intervention lying between the two. We will undertake mediator analysis to see if the identified pathways to effect measured at six months are associated with maintenance at one year.

An intention to treat analysis will compare the three groups on average BMI using a two level linear regression model to account for clustering within therapist. The main analysis will examine the longest end-point. A secondary analysis will examine the three groups using the interim time point as the end-point. Baseline BMI and previous weight loss will be included as covariates. Both of the intervention groups will be compared to the control in this model. If there is no evidence of clustering, then this will be reduced to a one level model. Secondary outcomes will be analysed similarly using either linear (e.g. diet, waist circumference) or logistic (e.g. probability of return to previous BMI) regression.

Exploratory analysis will consider the impact of demographic factors as well as original weight loss method and theoretical moderators on the intervention effect using interaction terms included in the main analysis models. Exploratory longitudinal analysis will be undertaken to explore the effect of theoretical mediators on subsequent outcomes and interactions with the intervention groups. Individuals lost to follow-up will be compared to those who complete follow up to identify any potential biases.

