A sensitivity analysis will be conducted where it will be assumed that all of those lost to follow-up returned to weight levels prior to weight loss (i.e. not baseline, but previous BMI). A Complier Adjusted Casual Effect (CACE) will also be estimated using multi-level mixture analysis. This modelling focuses on estimating the effect of the interventions in the presence of non-compliance, but also incorporates adjustments for loss to follow-up associated with the intervention. CACE approaches have been used in a number of studies of psychological therapies, using either relatively simple corrections through to the more complex multi-level mixture models proposed here. This provides a framework within which to model missingness rather than assuming missing at random (MAR).

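### The single full-regain sensitivity analysis for missing 12-month BMI is not reliably conservative, and it understates uncertainty if the assigned values are analysed as ordinary data

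*Protocol*

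**What the plan says.** Protocol section 11.1 specifies an intention-to-treat regression of 12-month BMI and adds that "Baseline BMI and previous weight loss will be included as covariates". It then describes one scenario for missing outcomes: "it will be assumed that all of those lost to follow-up returned to weight levels prior to weight loss", clarified as "i.e. not baseline, but previous BMI". The rule covers all arms. It gives no spread around the assigned value and no variance method.

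The same section also plans a complier-adjusted (CACE) mixture model that allows for loss to follow-up without assuming data are missing at random, and a comparison of those lost with those retained.

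On attrition, section 6.5 writes "Based on systematic reviews of similar studies we estimate that loss to follow-up will be around" 30%, with no figure by arm. Its retention measures differ by arm. Controls alone are offered £50 in vouchers or a free 12-week slimming programme "as an additional incentive to complete follow-up", while the intervention arms alone have continuing personal contact with staff.

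Section 2.1 gives a typical course: "around a third of the weight lost during an intervention is regained in the following year".

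**The concern.** Full regain looks like a worst case, so a reader will probably take it as a cautious bound. It is a bound on each dropout's BMI, not on the difference between arms. Because the same high value is used in every arm, the between-arm result depends on how many people each arm loses. If the intervention arm loses more, the estimate moves against the intervention; if control loses more, it moves in favour.

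The second issue is precision. Previous BMI is baseline BMI plus previous loss, exactly so if loss is entered in BMI units, and both are covariates. The assigned points therefore have almost no scatter of their own. Entered as ordinary data, they would count as fully known outcomes.

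The third is that one scenario cannot show how the estimate depends on assumed regain. This matters because sections 1.3 and 3.1 say the BMI results will indicate effect sizes for a larger trial, and section 11.1 commits to point estimates and confidence intervals for BMI.

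**Working it through.** **The plan's own figures.** 170 × 0.70 / 3 = 39.67, given as 39 per arm in section 10.2. The half-width 1.96 × √(0.25/n) is 15.7 percentage points at n = 39 and 7.5 at n = 170, as stated. The number lost is 170 × 0.30 = 51, about 17 per arm. The protocol gives no figure for the sensitivity analysis itself.

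**Size of the shift.** Let p_I and p_C be attrition in the intervention and control arms, L the mean earlier loss in BMI points, r the regain in control completers, and δ the true effect (negative is benefit). Measured as change from baseline, completers average r in control and r + δ in intervention, and every dropout is set to L. The expected estimate is

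(1 − p_I) × δ + (p_I − p_C) × (L − r).

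*Equal attrition of 30%:* 0.70 × δ. For δ = −1.0 this is −0.70 (simulated −0.69); for δ = −2.0 it is −1.40 (simulated −1.42). That is shrinkage of about 30%.

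*No true effect, control loses more, r = L/3 (section 2.1):* simulated with 56 per arm, two arms, a one-level model on baseline BMI and previous loss, residual SD 1.5 to 2.5, and 800 trials per scenario.

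| L (BMI points) | 25% v 35%: formula | simulated | 20% v 40%: formula | simulated |
|---|---|---|---|---|
| 2.67 | −0.18 | −0.16 to −0.20 | −0.36 | −0.35 |
| 4.05 | −0.27 | −0.25 to −0.27 | −0.54 | −0.53 to −0.57 |
| 6.0 | −0.40 | −0.39 to −0.40 | −0.80 | −0.80 to −0.82 |

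The null hypothesis was rejected in 6–14% of trials at 25% v 35% and in 13–41% at 20% v 40%.

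*True effect −0.58, either direction (57 per arm, residual SD 2, L = 10% of an assumed pre-loss BMI of 36 = 3.6, so L − r = 2.4):*

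- 30% in both arms: 0.70 × (−0.58) = −0.41 (simulated −0.42)
- intervention 35%, control 25%: −0.377 + 0.24 = −0.14 (simulated −0.13)
- intervention 40%, control 20%: −0.348 + 0.48 = +0.13 (simulated +0.15)
- intervention 25%, control 35%: −0.435 − 0.24 = −0.68 (simulated −0.67)
- intervention 20%, control 40%: −0.464 − 0.48 = −0.94 (simulated −0.93 to −0.95)

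**Scale.** Section 10.2 equates 3.537 BMI points with about 9.75 kg, or 2.757 kg per point. The two maintenance trials in section 2.1 found differences of 4.9 − 2.5 = 2.4 kg and 5.5 − 4.0 = 1.5 kg, which are 0.87 and 0.54 BMI points. The shift can be as large as a plausible effect.

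**Standard error.** Three analyses were compared: the fixed value treated as ordinary data, completers only, and multiple imputation centred on previous BMI with completers' residual scatter added. At 30% attrition in both arms (ratios from unrounded values):

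| Residual SD | L | Fixed value | Completers | Imputation | Fixed/completers | Fixed/imputation |
|---|---|---|---|---|---|---|
| 1.5 | 2.67 | 0.290 | 0.343 | 0.369 | 0.85 | 0.79 |
| 1.5 | 6.01 | 0.456 | 0.344 | 0.511 | 1.33 | 0.89 |
| 2.0 | 4.05 | 0.409 | 0.454 | 0.508 | 0.90 | 0.80 |
| 2.5 | 2.67 | 0.432 | 0.572 | 0.575 | 0.75 | 0.75 |
| 2.5 | 6.00 | 0.555 | 0.570 | 0.671 | 0.97 | 0.83 |

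Over all 27 scenarios, fixed/imputation ran from 0.75 to 0.89 and fixed/completers from 0.74 to 1.33. Point estimates were essentially the same under the fixed value and imputation. Therapist clustering was not simulated.

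**The case against.** The strongest reply is that this is a labelled stress test beside a main analysis and a CACE model, in a study that section 10.2 says is not mainly about effectiveness. The variance method is ordinary SAP content, and the SAP is not shown. If every dropout really did return to previous BMI, the analysis would be right: the model standard error then matches the spread over repeated trials (0.409 v 0.411), and a BMI difference arising from unequal dropout would be real.

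Much of this stands, and it rules out several stronger readings that a reader might infer:

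- That the protocol treats the assigned values as observed. It does not say so, and the point about precision is conditional on it.
- That the interval must be narrower than the completers' interval. It can be wider, because dropouts set to full regain lie off the completers' regression line and add residual variance in the pooled fit.
- That the control-only incentive fixes the direction of bias. Staff contact in the intervention arms pulls the other way, and no passage supports a particular attrition gap.
- That full regain contradicts the one third in section 2.1. That figure is an average after interventions, not a figure for dropouts, and a deliberately pessimistic scenario need not match it.

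The reply does not cover everything. The CACE model addresses non-compliance and adjusts for loss to follow-up, but it does not show how the estimate changes with assumed regain. The single scenario is fixed in the protocol whatever variance method is chosen.

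**Conclusion.** The point holds as a limited one. The rule gives one extreme scenario whose effect on the between-arm estimate has no predictable direction. It shrinks a true effect by about 30% when attrition is equal. For attrition gaps of 10 to 20 points it shifts the estimate by about 0.16 to 0.82 BMI points. If the assigned values are analysed as ordinary data, the standard error is about 11–25% below imputation under the same mean assumption.

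These sizes rest on assumed residual SDs of 1.5 to 2.5, mean earlier losses of about 2.7 to 6.0 BMI points, one third regained by completers, and the attrition splits shown. The protocol gives none of these except the one third and the overall 30%.

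A reader might go further and conclude that the main result is biased or its precision overstated. The documents do not support that, since section 11.1 presents this as a sensitivity analysis. This is a cheap and worthwhile improvement to a secondary analysis.

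**What to change.** Keep full return to previous BMI and label it as the extreme end of a range. Add multiple imputation of 12-month BMI from the main model, with the six-month self-assessed weight (section 9.1) as an auxiliary variable where available. Shift the imputed values for dropouts towards previous BMI by graded fractions of the weight lost, for example one third, two thirds and all, and let the fraction differ by arm. Report attrition by arm, and show how the point estimate and its multiple-imputation interval change across the grid, beside the planned CACE analysis. State in the protocol or SAP how uncertainty is attached to assigned values.

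The cost is a short paragraph of text and some analysis code, with no new data. The drawback is wider sensitivity intervals.

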# 11.2 Sub-group & interim analysis

Primary sub-group analyses will investigate associations between weight loss maintenance and age, gender, how much weight participants have lost, method of weight loss, and weight at entry. Exploratory sub-group analyses will investigate the association between weight loss maintenance and smokers, binge-eaters, participants who have been on weight-affecting medications during the trial and ethnicity.

## 11.3 Qualitative analysis and process evaluation

Data on intervention delivery and duration of participation in the intervention will be examined. The recorded MI sessions will be subject to analyses using the MITI scale to ensure they reach agreed standards. MI Case Report Forms (CRFs) from both face-to-face and telephone sessions (including session summaries given to participants) will be examined for evidence of self regulation, goal setting and implementation intentions. These will be analysed descriptively. The interviews and focus groups will be analysed using framework analysis techniques. This method of analysis is essentially a process of summarisation, categorisation and counting frequency of responses. The transcripts will be

closely examined to identify themes and categories. Codes will be applied to these broad themes which will then be broken down further into sub-codes. Agreement on concepts and coding will be sought between members of the research team in order to ensure reliability. We will seek to identify commonly expressed themes as well as unusual cases. A proportion of the data (10%) will be coded by two different team members to check on reliability of the coding scheme. The interviewing will be iterative; where new themes emerge we will incorporate them into the interviews. Analysis will be supported by the use of computer assisted qualitative analysis software (NVIVO).

#### 11.4 Economic evaluation

There are limitations to undertaking a cost utility analysis within a feasibility study. Although we will not be able to establish definitive cost utility results, we will apply a cost utility framework to estimate parameters and unknowns for future research. Direct costs will include all resources used in the delivery of the interventions (staff time, staff travel, materials, venue, etc.). These will be recorded prospectively in relevant units and valued using standard methods. All resources used in training professionals in motivational interviewing skills will similarly be prospectively recorded and valued. As training is a one off investment which produces a flow of benefits over time, training costs will be amortised similarly to equipment expenditures.

Indirect costs will include differential use of NHS resources. Health service resource use in primary care, secondary care and the community will be collected for participants in all 3 arms of the trial at baseline, 6 months (during the intervention) and at 12 months. Questions will relate to all health service contacts and prescription medicines dispensed in the previous 3 months. Patient recall has been shown to be a valid method for collecting health service resource use data over this period. Health service resource use will be valued using standard sources. All costs relating to weight loss/maintenance activities such as use of gyms will be recorded. It is important to monitor these costs as the intervention may be substituting for some activities, for example weight loss group sessions by participants in the control group. Mean differential costs will be estimated. As cost data are often skewed, tests for normality will be applied. If distributions are shown to be nonnormal, non-parametric bootstrapping methods will be used to test for mean cost differences between groups.

The main effectiveness measure in the economic evaluation will be the EQ-5D (EuroQol) quality of life instrument which will be administered alongside the resource use questionnaire. EQ-5D scores allow estimation of quality adjusted life years (QALY). Cost effectiveness will be based on between group differences in costs and EQ-5D scores. This is the method of economic evaluation preferred by NICE as the resulting cost utility estimates can be compared not only with other weight control programmes, but also with unrelated health care interventions. Results will be reported in the form of incremental cost utility ratios (incremental cost/QALY). A cost effectiveness acceptability curve will show the probability of the more costly intervention having an incremental cost utility ratio below a range of acceptability thresholds. A series of one way and multivariate sensitivity analyses will be undertaken to assess how sensitive results are to changes in the assumptions used and these analyses will be key given that this is a feasibility study.

At present, there is a paucity of evidence on how changes in BMI are related to changes in EQ-5D. We will therefore undertake a secondary analysis with BMI as the effectiveness

measure. Difference in the two analyses will contribute to the evidence on the relationship between these two measures.

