| Body Composition                  |                    |            |           |  |
| BMI (weight & height)                    | Calibrated digital | B, 12m     | 2 minutes |  |
|                                          | scales &           |            |           |  |
|                                          | stadiometer        |            |           |  |
| Waist and hip circumferences             | Tape               | B, 12m     | 3 minutes |  |
| Other                                    |                    |            |           |  |
| Physical activity                        | IPAQ  | B, 12m     | 5 minutes |  |
| Diet                                     | DINE  | B, 12m     | 5 minutes |  |
| HR quality of life                       | $EQ5D^{34}$        | B, 6m, 12m | 1 minute  |  |
| Health and other resource usage          | Case Report Form   | B, 6m, 12m | 4 minutes |  |

| Proportion maintaining weight |                       | 12m    |           |
|-------------------------------|-----------------------|--------|-----------|
| loss                          |                       |        |           |
| Binge eating                  | EDE-Q    | B, 12m | 1 minute  |
| Psychological well being      | GHQ12    | B, 12m | 3 minutes |
| Health-related behaviours     | AUDIT-C &             | B, 12m | 2 minutes |
| (alcohol consumption &        | HSI  |        |           |
| smoking status)               |                       |        |           |

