#### 10 Statistical considerations

#### 10.1 Randomisation

Allocation to groups will be by remote telephone randomisation and stratified by region (Primary Care Trust) and minimized by age, gender, ethnicity, source of recruitment (exercise referral scheme, community, etc), % weight loss and current BMI. Whoever is recruiting the potential participants will call the randomisation telephone number and the participant will be given an information pack detailing the next steps.

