#### 10.2 Sample size

The sample size for the original study was 950 and based on detecting an effect size of 0.309 with 90% power at a significance level of 5%. Since this is now a feasibility study, the planned sample size will not be derived statistically. Instead the intended sample size is the number of participants it is possible to recruit based on our inclusion criteria over an 18 month period. Since recruitment has now closed our potential sample size is 170. This sample size allows us to estimate a percentage of 50% (the percentage with the greatest associated variability) to within 7.5 percentage points either side for the whole sample (n= 170), or to within 15.7 percentage points for percentages within each study arm (n = 39). These are the precisions that will be achievable for the estimation of the retention rate or any other proportion. As a feasibility study we are not primarily concerned with effectiveness, however we still feel it is informative to present the power we will have to detect differences. With our current sample size (n=170) and assuming 30% attrition, we have 39 in each of the three treatment arms. We will be able to detect a difference of 3.537 BMI points at the 5% significance level with 80% power between any two arms (our primary comparison was between the control group and the intensive arm). This is just over a difference of 9.75kgs between groups.

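### The economic evaluation names no adjustment for baseline EQ-5D or baseline resource use, although both are collected; adding it would sharpen the cost-utility estimates at no cost

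*Protocol*

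**What the plan says.** Section 11.4 gives the basis of the cost-utility comparison: "Cost effectiveness will be based on between group differences in costs and EQ-5D scores". It links the instrument to the outcome by noting that "EQ-5D scores allow estimation of quality adjusted life years (QALY"), but gives no QALY formula. For costs it plans to estimate mean differences, with a normality check and bootstrapping where that fails. Results are to appear as incremental cost per QALY with an acceptability curve and sensitivity analyses.

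The baseline data exist. Health service resource use "will be collected for participants in all 3 arms of the trial at baseline, 6 months (during the intervention) and at 12 months", and the EQ-5D row of Table 1 in section 8.1 reads "B, 6m, 12m | 1 minute".

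Allocation (section 10.1) is stratified by region and "minimized by age, gender, ethnicity, source of recruitment (exercise referral scheme, community, etc), % weight loss and current BMI". EQ-5D is not among these factors.

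Section 11.1 names baseline BMI and previous weight loss as covariates in the BMI model and says that secondary outcomes are handled in a similar way by regression. It names neither baseline EQ-5D nor QALYs or costs. Section 10.2 gives the expected arm size: "With our current sample size (n=170) and assuming 30% attrition, we have 39 in each of the three treatment arms".

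**The concern.** Section 11.4 describes how differences will be formed and tested, and no baseline term appears anywhere in that description. Where the protocol wants covariates, as for BMI, it names them.

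Utility at entry matters twice for a one-year QALY. It is one of the three points on the curve, and it predicts the other two. Baseline resource use covers the three months before entry, so it cannot be an effect of the intervention; its natural role in the comparison is as a covariate, and section 11.4 gives it none.

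The stated purpose of the economic work is to supply parameters for future research. If the comparison is left unadjusted, the incremental QALY and the acceptability curve would be noisier than the collected data require, and in the sample actually drawn they would partly reflect which arm was healthier at entry.

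**Working it through.** **Arm size.** 170 × 0.70 / 3 = 39.67, which the protocol truncates to 39. The figure reproduces.

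**Assumptions not in the protocol.** QALYs by the trapezoid rule over 0, 6 and 12 months, giving weights 0.25, 0.5 and 0.25; the same SD at each visit; the same correlation r between any two visits, taken as 0.5 to 0.7; EQ-5D SD 0.25, with a range of 0.15 to 0.30.

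**Chance imbalance at baseline.** SE of the difference between two arm means = SD × √(2/39) = 0.226 SD. The 95% range is ±1.96 × 0.226 = ±0.444 SD. At SD 0.25 the SE is 0.057 and the 95% range ±0.111. Across SD 0.15 to 0.30 the SE runs from 0.034 to 0.068.

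**Share that enters the QALY difference.** Regression slope of the QALY on baseline EQ-5D = 0.25 + 0.75r.
- r = 0.5: 0.25 + 0.375 = 0.625
- r = 0.7: 0.25 + 0.525 = 0.775

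So about 63% to 78% is carried over: 25 points directly through the baseline weight, the rest through correlation. At SD 0.25 an imbalance of one SE moves the expected QALY difference by 0.057 × 0.625 = 0.035 to 0.057 × 0.775 = 0.044. At SD 0.15 with r = 0.5 the shift is 0.034 × 0.625 = 0.021; at SD 0.30 with r = 0.7 it is 0.068 × 0.775 = 0.053.

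**Precision with and without adjustment**, in units of SD². Unadjusted QALY variance = 0.375 + 0.625r. Adjusted variance = unadjusted variance − slope².

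| r | Unadjusted variance | Slope² | Adjusted variance | SE ratio | Reduction in SE |
|---|---|---|---|---|---|
| 0.5 | 0.6875 | 0.3906 | 0.2969 | √(0.2969/0.6875) = 0.66 | 34% |
| 0.7 | 0.8125 | 0.6006 | 0.2119 | √(0.2119/0.8125) = 0.51 | 49% |

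The SD cancels from the ratio, so the percentage reduction does not depend on it. At SD 0.25, SE = 0.25 × √variance × 0.226 gives 0.047 (r = 0.5) and 0.051 (r = 0.7) unadjusted, against 0.031 and 0.026 adjusted. Baseline EQ-5D accounts for 0.3906/0.6875 = 57% to 0.6006/0.8125 = 74% of the sampling variance of the unadjusted QALY difference.

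**Wider range of r.** At r = 0.4 the SE ratio is 0.72 (28% reduction); at r = 0.8 it is 0.42 (58% reduction).

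**If only 12-month scores are compared.** The SE ratio is √(1 − r²): 0.87 at r = 0.5 and 0.71 at r = 0.7, a reduction of 13% to 29%. The share of the imbalance carried over is then r itself.

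**Costs.** The protocol gives nothing from which to size the gain from adjusting costs, so no figure is offered.

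**The case against.** A reader might infer that section 11.4 prescribes a raw, unadjusted comparison. The text does not go that far. It names the quantities compared, and a regression-adjusted arm difference is still a between-group difference. Section 11.1 sends secondary outcomes, which include health-related quality of life, to regression in the manner of the BMI model; that weighs against a deliberate choice to ignore baseline. A statistical or health economics analysis plan, not shown here, could settle the estimator. All of this stands. What remains is that section 11.4 describes its own estimation route for QALYs and costs without a baseline term, and that the general sentence in section 11.1 does not expressly reach either.

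A reader might also infer that an imbalance passes through in full, or that the unadjusted result is biased. Neither holds. Under the assumptions above, 22% to 38% of a baseline difference does not carry over. Randomisation keeps the unadjusted difference unbiased over repeated trials; the loss is in precision and in bias conditional on the sample drawn. Minimising on age, BMI and the other factors may balance utility indirectly to the extent that they correlate with it, but the protocol gives no figure for that.

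Finally, the protocol calls the cost-utility analysis preliminary and not definitive, and plans sensitivity analyses. No adoption decision rests on it. That limits the consequence, but precision still matters when the purpose is to estimate parameters.

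**Conclusion.** The point holds as a free improvement, not as an error or a contradiction. Section 11.4 names no adjustment for baseline EQ-5D or baseline resource use, both are collected, and EQ-5D is not a minimisation factor. With 39 per arm, an unadjusted QALY difference would be expected to carry about 63% to 78% of any baseline EQ-5D difference, and adjustment would reduce its standard error by about 34% to 49%, or by 13% to 29% for 12-month scores alone. These percentages rest on the assumed correlation of 0.5 to 0.7, on equal SDs across visits and, for the QALY figures, on the trapezoid rule. The absolute QALY amounts also rest on an assumed SD and vary two-fold between SD 0.15 and SD 0.30.

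**What to change.** State in section 11.4, or in the analysis plan with a cross-reference from it, that:

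- QALYs are the area under the EQ-5D curve at baseline, 6 and 12 months;
- arm differences in QALYs are estimated by regression on arm with baseline EQ-5D as a covariate;
- arm differences in cost are estimated in the same way, with baseline resource cost as a covariate;
- these adjusted differences, re-estimated within each bootstrap sample, feed the cost-utility ratio and the acceptability curve.

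The cost is a few sentences of text. The baseline data are already collected, and neither the sample size nor the visit schedule changes. If adjustment was always intended, this is only a clarification.
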